10.1.2 Missing Data Imputation for Efficacy Endpoints

No imputation of missing data is planned for the primary and secondary endpoints of this study. For TTE, if the event of interest is not observed for a subject in the study, such as when the subject is lost to follow-up, the endpoint will be right censored at the last adequate observation time when occurrence of an event can be ruled out. For patient reported outcomes (PRO) including MDASI-BT symptom score, QLQ-C30, and QLQ BN20, the imputation strategies will be based on the scoring manuals and no additional imputation will be done.

10.2 Primary Efficacy Analysis

The primary endpoint OS will be compared between treatment arms Depatux-M + RT/TMZ and Placebo + RT/TMZ. Superiority of Depatux-M + RT/TMZ to Placebo + RT/TMZ in terms of OS will be evaluated using stratified weighted log-rank test, adjusting for the study stratification factors. Recently available data from the

INTELLANCE-2 trial²⁷ as well as published studies on GBM patients^{22,25} suggest increasing separation over time. To account for the possibility of late separation in OS (and consequently, non-proportional hazards), use of a weighted log-rank test in a pre-specified manner is considered to be a more appropriate and statistically efficient test to detect statistical differences in OS compared to the standard log-rank test. Under the weighted log-rank test, each event is weighted differently based on timing of the events from randomization. The Fleming-Harrington (FH) version of weighted log rank test¹⁰ will be used with following weight function:

$$w(t|\rho, \gamma) = [\hat{S}_{KM}(t)]^\rho [1 - \hat{S}_{KM}(t)]^\gamma, \quad \rho, \gamma \geq 0$$

where, $\hat{S}_{KM}(\cdot)$ is the KM estimate of the survival function in the pooled data. The events that occur later in the study should get more weights to account for late separation. This can be achieved with parameters, $\rho = 0$ and $\gamma > 0$. In this study, we pre-specify $\rho = 0$ and $\gamma = 0.2$ for the FH weights in the weighted log-rank test.

The Fleming-Harrington (FH) version of weighted log-rank tests are well recognized statistical methods that do not inflate the type 1 error if pre-specified.^{9,24} The hazard-ratio of OS for Depatux-M + RT/TMZ compared to Placebo + RT/TMZ will be estimated by fitting Cox-proportional hazards regression models adjusting for the main-effects of the stratification factors.

This FH test will be implemented in SAS using LIFETEST procedure as follows:

```
proc lifetest method=km;
  time <follow-up time>*<Censoring status>(<censoring codes>);
  strata <stratification factors> / group=<treatment>
      test=FLEMING(0, 0.2) trend;
run;
```

The hazard-ratio of OS for Depatux-M + RT/TMZ compared to Placebo + RT/TMZ will be estimated by fitting Cox-proportional hazards regression models adjusting for the main effects of the stratification factors. Treatment difference in restricted mean survival time (RMST) up to 24 and 30 months will also be estimated.

Estimation of HR

A Cox proportional-hazards regression model⁶ with the treatment and stratification factors as covariates will be used to estimate the HR of Depatux-M + RT/TMZ to Placebo + RT/TMZ and its two-sided 95% CI:

$$\lambda(t|\text{treatment, stratum } s) \\ = \lambda_0(t) \cdot \exp(\theta \cdot \text{treatment} + \phi_1 \cdot x_1 + \phi_2 \cdot x_2 + \phi_3 \cdot x_3 + \phi_4 \cdot x_4)$$

where, treatment takes value 1, if treated with Depatux-M + RT/TMZ, otherwise 0, for Placebo + RT/TMZ. x_1, x_2, x_3 and x_4 represent the coefficient for the 4 stratification factors, namely, region of the world, RPA class, MGMT methylation status, and EGFRvIII status. The estimated value of $\exp(\theta)$ represents the hazard ratio on Depatux-M + RT/TMZ (adjusting for the effect of stratification factors) compared to Placebo + RT/TMZ. Effron's approximate method (1977) will be used for handling ties. In SAS, the estimate of HR will be estimated using PHREG procedure and Effron's method⁷ will be employed by using TIES = EFFRON option in MODEL statement.²⁰ The following SAS code will be used

```
PROC PHREG;  
  CLASS <treatment> <strata variables>;  
  MODEL <follow-up time>*<Censoring status>(<censoring codes>)=  
<treatment> <strata variables>/TIES=EFFRON RL;  
RUN;
```

Supportive analysis: Difference in restricted mean survival time (RMST)

RMST up to 24 months and 30 months will be reported in each treatment arm separately. Difference between treatment arms will also be reported. RMST is expressed as

$$E[\min(\text{OS time}, t^*)] = \int_0^{t^*} S(t) dt$$

where t^* (24 or 30) represents the restriction. In SAS, RMST will be calculated using TIMELIM option in LIFETEST procedure as follows after censoring the largest observation:

```
PROC LIFETEST TIMELIM=<24 or 30>;  
  TIME <follow-up time>*<Censoring status>(censoring codes);  
  STRATA <treatment>;  
RUN;
```

10.3 Secondary efficacy analysis

Secondary efficacy endpoints are defined in Section 5.3.2. Each of the following secondary efficacy endpoints will be analyzed in the order it is mentioned:

1. PFS per central assessment
2. OS for the MGMT unmethylated subgroup
3. OS for the MGMT methylated subgroup
4. Deterioration free survival in MDASI-BT symptom severity score
5. Deterioration free survival in MDASI-BT symptom interference score
6. Deterioration free survival in HVL-T-R total recall score
7. OS for the EGFRvIII-mutated tumor subgroup
8. PFS (assessed centrally) for the EGFRvIII-mutated tumor subgroups

OS for the EGFRvIII-mutated tumor subgroup will be analyzed in the subset of FAS using stratified weighted log-rank test (FH ($\rho = 0$, $\gamma = 0.2$)) with stratification factors as region of the world, RPA classes and MGMT methylation status. OS for the MGMT methylated subgroups will be analyzed in the subset of FAS using stratified weighted log-rank test (FH ($\rho = 0$, $\gamma = 0.2$)) with stratification factors as region of the world, RPA classes and EGFRvIII status.

Remaining secondary endpoints (#1, #4, #5, #6, and #8 in the above list) will be analyzed in the FAS using the standard stratified log-rank test. Standard log-rank test will be carried out in SAS using PHREG procedure specifying TEST = LOGRANK and TREND option in the STRATA statement as follows:

```
proc lifetest method=km;  
  time <follow-up time>*<Censoring status>( <censoring codes> );  
  strata <stratification factors> / group=<treatment>  
      test=LOGRANK trend;  
  
run;
```

10.4 Other efficacy analyses

10.4.1 Additional analyses based on OS, centrally assessed PFS and local investigator assessed PFS

Kaplan-Meier (KM) estimate of OS rates and centrally assessed PFS rates at 0.5, 1, 2, 2.5, 3, 4, and 5 years will be determined for each treatment group along with 95% confidence intervals (CIs) based on Greenwood's method. Estimates will be provided both in overall population and for the subgroups based on stratification factors.

PFS per local investigator assessment will be analyzed using the same statistical methodology as that for the centrally assessed PFS described in Section 10.3.

10.4.2 Analyses of QLQ-C30 and QLQ-BN20 response

Change from baseline in Global Health Status score, Physical Functioning, Cognitive Functioning, Role Functioning in QLQ-C30 questionnaire

Change from baseline in Visual Disorder, Motor Dysfunction, and Communication Disorder scale in QLQ-BN20 questionnaire

Baseline data along with post-baseline and change from baseline at each visit will be descriptively summarized. The treatment group differences will be evaluated by analyzing the change from baseline to each of the post-baseline time-point and to the final measurement (last QoL assessment per subject) using an analysis of covariance

(ANCOVA) model adjusting for baseline and stratification factors. Treatment difference along with 95% confidence interval will be provided.

10.4.3 Analysis of EQ-5D-5L index value and EQ VAS score

Change from baseline in EQ-5D-5L index value and EQ VAS score will be analyzed in a similar way to that described in "Change from baseline" in Section [10.4.2](#).

10.4.4 Analysis of COWA-FAS verbal fluency score

Verbal fluency score obtained from COWA-FAS verbal fluency test will be analyzed for change from baseline by using methods described in Section [10.4.2](#).

Deterioration Free Survival in verbal fluency score will be analyzed in the FAS using the standard stratified log-rank test with stratification factors as region of the world, RPA classes, MGMT methylation status, and EGFRvIII status.

10.4.5 Additional analysis of HVLТ-R scores

Total Recall score, Delayed Recall score and Recognition Discrimination Index obtained from HVLТ-R will be analyzed separately for change from baseline, by using methods described in Section [10.4.2](#).

10.4.6 Analysis of KPS score

KPS score will be analyzed for change from baseline by using methods described in Section [10.4.2](#). Time-to- KPS < 70 will be analyzed by the standard stratified log-rank test with stratification factors as region of the world, RPA classes and EGFRvIII status. In addition, median time to KPS score was maintained at 70 or higher will be obtained for each treatment arm through Kaplan-Meier analysis considering death, progression, or KPS < 70 as event.

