14.2 Statistical Methods

This is a comparative randomized, placebo controlled, double-blinded Phase 3 trial. All efficacy analyses will be performed in the Full Analysis Set (defined below). OS (primary efficacy endpoint for the overall study) and PFS (secondary efficacy endpoint) will be compared between treatment Arms A and B using stratified log-rank test statistics or a weighted version of this test (to be pre-specified in the Statistical Analysis Plan document (the SAP)), adjusting for the study stratification factors. PFS is defined as time from randomization to progression of disease (per RANO criteria) or death, whichever occurs first.

Randomization and Stratification

MGMT methylation status and RPA (referenced in [Appendix VI](#)) are demonstrated to be prognostic of survival for newly diagnosed GBM subjects. For this study, subjects will be stratified by *MGMT* methylation status (methylated versus unmethylated), RPA class (III versus IV versus V), region of the world (US/Canada versus other) and *EGFRvIII* mutation status (mutated versus other), where *EGFRvIII* other is defined as wild type, indeterminate due to test failure, invalid, or insufficient tissue. *EGFRvIII* is a stratification factor because it is potentially prognostic and because it is related to the mechanism of action of ABT-414 which binds to both activated wild type *EGFR* and *EGFRvIII*. After stratification, subjects will be randomized to either Arm A or Arm B in a 1:1 ratio.

Analysis Sets

The following analysis sets will be used for analysis of safety and primary and secondary efficacy endpoints of the study:

- Full Analysis Set (FAS) will comprise all randomized subjects regardless of whether they received study treatment. Subjects will be classified according to the treatment they were assigned at the time of randomization. The FAS will be the primary analysis set for the analysis of efficacy endpoints.

- Safety Analysis Set (SAS) will comprise all randomized subjects who receive at least one dose of study treatment (either RT, TMZ or ABT-414). Subjects will be classified according to treatment received. Thus a subject randomized to Arm A who receives RT+TMZ but does not receive ABT-414 will be considered in the control group (Arm B) for safety analysis.

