5.2.2 Variables used for Stratification at Randomization

All screening activities must be completed and reviewed prior to randomization. Subjects who meet the eligibility criteria will be stratified according to the following 4 factors:

- *MGMT* methylation status: Methylated and Unmethylated
- RPA classes: III, IV, and V
- Region of the World: North America (includes USA and Canada) and Rest of the World (ROW)
- *EGFRvIII* status: Mutated and Other.

EGFRvIII Other includes wild type, indeterminate due to test failure, invalid, or insufficient tissue. Within each stratum, subjects will be randomized to either Arm A (i.e.,

Depatux-M + TMZ) or Arm B (i.e., Placebo + TMZ) in a 1:1 ratio via the interactive response technology (IRT) system.

Screening numbers will be unique 5-digit numbers with the first 3 digits representing the investigative site, and the last 2 digits representing the subjects at that site. Randomized subjects will keep their screening number as their subject identification number. During randomization each patient will receive a separate unique 6 digit randomization number. This randomization number will be recorded automatically in the electronic case report forms (eCRFs) through the IRT system.

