6.1 Definition of Analysis Populations

6.1.1 Efficacy Populations

Full Analysis Set (FAS) will comprise all randomized subjects regardless of whether they received study treatment satisfying the following criteria:

- Enrollment date was on or prior to 31-Mar-2018
- Enrolled in the main study (not in the open-label hepatic sub-study)

Subjects will be classified in the treatment groups, "Depatux-M + RT/TMZ" or "PBO + RT/TMZ," according to the treatment they were assigned at the time of randomization. Unless otherwise specified (and except for subgroup and sensitivity analyses), the FAS will be the default dataset for analysis of efficacy data.

Per-protocol Set (PPS) will be comprised of a subset of patients in FAS. Subjects meeting any of the following criteria will be excluded from PPS:

- Those entered into the study even though did not satisfy the entry criteria
- Those who developed withdrawal criteria during the study but were not withdrawn
- Those who received the wrong treatment
- Those who received an excluded concomitant treatment

Subjects will be classified according to treatment assigned.

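### SAP 10.4.6 leaves MGMT out of the strata for the exploratory time-to-KPS<70 log-rank test, so the p-value and the hazard ratio for that endpoint adjust for different factors

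*SAP*

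**What the plan says.** SAP 10.4.6 contains three KPS analyses: change from baseline by the method of 10.4.2, a test of time to KPS < 70, and a median time at KPS 70 or higher. The test is a "standard stratified log-rank test with stratification factors as region of the world, RPA classes and EGFRvIII status". The median is obtained "through Kaplan-Meier analysis considering death, progression, or KPS < 70 as event".

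SAP 5.2.2 describes the randomisation: "Subjects who meet the eligibility criteria will be stratified according to the following 4 factors". They are MGMT methylation (2 levels), RPA class (3), region (2) and EGFRvIII status (2).

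These passages bear on the same choice:

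- SAP 10.4.4, COWA-FAS deterioration-free survival, another exploratory log-rank test in the FAS: "with stratification factors as region of the world, RPA classes, MGMT methylation status, and EGFRvIII status".
- SAP 10.2, the Cox model for OS, whose covariates "represent the coefficient for the 4 stratification factors, namely, region of the world, RPA class, MGMT methylation status, and EGFRvIII status".
- SAP 10.1.1, the general rule for time-to-event endpoints: log-rank tests are stratified as each section specifies, and hazard ratios come from a Cox model with main effects of the stratification factors, none excluded.
- SAP 10.3: "OS for the MGMT methylated subgroups will be analyzed in the subset of FAS", with region, RPA class and EGFRvIII as strata.
- SAP 6.1.1: unless otherwise specified, and apart from subgroup and sensitivity analyses, "the FAS will be the default dataset for analysis of efficacy data".
- Protocol 14.2: MGMT status and RPA class "are demonstrated to be prognostic of survival for newly diagnosed GBM subjects".

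**The concern.** A stratified log-rank test normally uses the factors that define the randomisation strata. Here one of the four is missing, and it is one of the two that the protocol singles out as prognostic for survival. The other, RPA class, is kept.

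Two things follow. First, the p-value and the hazard ratio for one endpoint would rest on different adjustments, which is awkward to report and to explain. Second, if MGMT is prognostic for this endpoint, leaving it out can cost a little power.

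The paragraph also does not say which event the test counts. It names time to KPS < 70, then gives a composite of death, progression or KPS < 70 for the median. A programmer cannot tell from the text whether the composite also applies to the test.

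**Working it through.** **Is the omission explained anywhere?** Three-factor lists also appear in SAP 10.3, but each belongs to a subgroup in which the dropped factor is constant. The list of region, RPA class and EGFRvIII is used there for OS in the MGMT methylated subgroup, where stratifying by MGMT would do nothing. SAP 10.4.6 names no subgroup, so the FAS applies and MGMT varies. The general rule in 10.1.1 defers to what each section specifies, so it does not put MGMT back.

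**Number of strata.** The plan states no count, sample size or power for this analysis, so there is no figure to reproduce.

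- As written: 2 (region) × 3 (RPA) × 2 (EGFRvIII) = 12 at most, or 639/12 ≈ 53 subjects each.
- With MGMT: 12 × 2 = 24 at most, or 639/24 ≈ 27 each.

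**Effect on power, by simulation.** 10,000 trials per scenario, N = 639, permuted blocks of 4 within the 24 cells, one-sided 0.025.

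- From the documents: follow-up uniform over 13 to 42 months (enrolment closed 31 March 2018 and data cut 30 April 2019 give 13; adding the projected 29-month accrual gives 42); PFS medians of 6.3 and 8.0 months; treatment HR 0.75, borrowed from the OS design.
- Assumed: 35% methylated; RPA III/IV/V at 15/60/25% with HR 0.7/1/1.5; region and EGFRvIII split evenly with no effect; exponential times; a 20-month median for KPS < 70; KPS follow-up ending 35 days after progression, with PFS unrelated to MGMT; and every MGMT hazard ratio.

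| Assumed MGMT HR | KPS < 70 alone (161–168 events): 12 v 24 strata, power % | Change (points) | Composite (557–570 events): 12 v 24 strata, power % | Change (points) |
|---|---|---|---|---|
| 1.0 | 42.4 v 41.4 | -1.1 | 91.5 v 90.4 | -1.1 |
| 1.5 | 42.4 v 41.3 | -1.2 | 90.7 v 90.8 | 0.0 |
| 2.0 | 42.6 v 43.0 | +0.4 | 88.2 v 90.7 | +2.6 |
| 2.5 | 41.2 v 42.3 | +1.1 | 85.6 v 90.9 | +5.3 |

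Changes come from unrounded powers and can differ by 0.1 from the table. Their Monte Carlo standard error is 0.2 to 0.3 points.

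If MGMT also drives progression, and PFS is 6.3 v 8.0 months by arm, the changes for KPS < 70 alone become -0.7 / +0.7 / +3.1 / +5.1 points. Varying the methylated share over 25/45/55% at MGMT HR 2.0 gives +0.3 / +0.4 / +0.3 points (KPS alone) and +1.8 / +2.5 / +3.0 points (composite).

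**Type I error.** With treatment HR 1.0 the rejection rates were:

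- KPS alone: 0.0226–0.0265 with 12 strata, 0.0231–0.0278 with 24.
- Composite: 0.0195–0.0257 with 12 strata, 0.0244–0.0278 with 24.

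The standard error is 0.0016, so the highest value is (0.0278 - 0.025)/0.0016 ≈ 1.75 standard errors above nominal. Neither version inflates the error. The 12-strata test turns slightly conservative only for the composite.

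**Cross-check with a simpler model.** 2,000 runs, one event with a 10-month median in unmethylated placebo subjects, uniform censoring at 6 to 36 months, methylated-group HR 0.7 / 0.5 / 0.4. Power with 24 v 12 strata was 81.2 v 80.9, 78.0 v 75.5 and 75.7 v 73.8%, a gain of about 0 to 3 points.

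**The case against.** The case for leaving the text alone has real substance.

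- No stated rule is broken. SAP 10.1.1 lets each section specify its strata, and a test with fewer strata is valid. This stands: the point is one of consistency, not validity.
- MGMT is already handled in the effect estimate, through the Cox rule in 10.1.1. This stands too. It narrows the issue to the p-value, but it is also what makes the p-value and the hazard ratio disagree on adjustment.
- For the event that 10.4.6 names for the test, KPS < 70, adding MGMT makes almost no difference, and it loses about 1 point in two of the four scenarios. This stands and sets the size of the point.
- Protocol 14.2 calls MGMT prognostic of survival, not of KPS decline. This is correct, and it is why the MGMT effects above are labelled as assumptions.

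A reader might infer that the test disregards the randomisation. It does not: three of the four factors are kept, and the 12 cells are unions of the 24 randomisation cells.

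A reader might also take the share of simulated trials in which the 0.025 decision changes as evidence of harm. For KPS < 70 alone that share is 6.1–7.0%, but it is 6.4% when MGMT has no effect at all, so it is essentially noise.

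It is also tempting to say that the list was copied from the MGMT subgroup text in 10.3. That is plausible, but the SAP does not say so.

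**Conclusion.** The omission is clear from the text and unexplained, and it is worth correcting as a minor consistency point. It affects one exploratory p-value, tested at a nominal one-sided 2.5% outside the multiplicity hierarchy (SAP 10.1). The Kaplan-Meier median by arm, the primary and secondary results, and type I error control are untouched.

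The expected change from adding MGMT is about -1 to +1 point of power for KPS < 70 alone. A reader might infer a routine loss of 3 to 5 points. The documents do not support that: gains of that size need either the composite event or an MGMT effect on progression, together with MGMT hazard ratios of 2.0 to 2.5, and the documents give no MGMT effect for this endpoint. Confidence is high on the discrepancy in the text and low on the exact change in power.

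**What to change.** In SAP 10.4.6, add MGMT methylation status so that the test is stratified by all four randomisation factors, as in 10.4.4. If the omission is deliberate, state the reason. In the same sentence, say whether the test's event is KPS < 70 alone or the composite of death, progression or KPS < 70 used for the median.

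This takes a few words and needs no new data or subjects. The possible cost is about 1 point of power if MGMT is only weakly prognostic for this endpoint. Because interim efficacy results are already reported in Protocol 1.0, a change made now should be recorded as a clarification after unblinding, not presented as pre-specified.

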10.4.7 Additional analyses for MDASI-BT symptom severity score

Following endpoint will be analyzed in a similar way to that described in "Change from baseline" in Section [10.4.2](#):

- Change from baseline in MDASI-BT symptom severity score
- Change from baseline in MDASI-BT symptom interference score
- Change from baseline in neurologic domain score
- Change from baseline in cognitive domain score
- Change from baseline in treatment domain score
- Change from baseline in Vision item score (one of the 9 brain tumor-specific items)
- Change from baseline in MDASI-BT activity-related score
- Change from baseline in MDASI-BT mood-related score

10.4.8 Analysis of corticosteroid use data

Change from baseline in average daily (dexamethasone equivalent) corticosteroid dosing during the treatment period will be analyzed in a similar way to that described in "Change from baseline" in Section [10.4.2](#).

10.5 Sensitivity Analyses

Sensitivity analyses will be conducted to evaluate the robustness of efficacy results. PFS and OS will be analyzed in the PPS using the same statistical methodology.

The primary endpoint of OS will be analyzed based on a stratified log-rank test, adjusting for the study for the study stratification factors.

Two sensitivity analyses will be carried out for PFS endpoint by implementing different censoring rules in the definition of PFS (i.e., modified PFS endpoint). These sensitivity analyses will be conducted in the FAS population using the same statistical methodology as that for the PFS endpoint described in Section [10.3](#).

Sensitivity analysis 1: PFS as time from randomization to the date of progression of disease (PD) assessed centrally per RANO criteria or death, whichever occurs first. Subjects without an event will be right-censored at the date of last follow up for disease progression.

Sensitivity analysis 2: PFS as time from randomization to the date of progression of disease (PD) assessed centrally per RANO criteria or death, whichever occurs first. Subjects with 2 or more consecutive missed assessments (i.e., > 20 weeks since last RANO assessment) without any subsequent assessment prior to the PFS event (i.e., progression or death) will be considered progressed at the planned date of the earliest missed RANO assessment (i.e., last scan date prior to event + 8 weeks). Subjects without an event will be right-censored at the date of last follow up for disease progression.

As a sensitivity analysis, at each post-baseline assessment, change in standardized HVLTR total recall score relative to baseline will be calculated and categorized as deteriorated or not using the reliable change index (RCI) criterion based on the raw scores. The details are provided in Appendix I. Deterioration free survival in HVLTR total recall score (using the RCI criterion) will be analyzed using the stratified log-rank test.

